## 5 STUDY INTERVENTIONS

### 5.1 Two Point Discrimination Training:

Two-point discrimination threshold (TPD) training may be performed 1) at spatial locations remote from pain, 2) at spatial locations adjacent to the region of pain, and/or 3) at spatial locations in the site of pain, if the participant will tolerate it. TPD is defined as the smallest distance between two points at which someone can recognize two points, and not one, touching their skin. As such this is a test of one's ability to identify separate stimulation of two discrete areas, and relies heavily on lateral inhibition. Highly

precise mechanical calipers will be gently placed onto the skin and the distance between the prongs will be increased/decreased. After repeated decreases and increases in the distance between the prongs, the TPD will be deemed as the distance at which participants consistently report two points instead of one (Moseley et al., 2008,)(Wand et al., 2010). One-point stimuli will be interleaved to serve as a control condition. Participants will be informed immediately of correct and incorrect responses as part of the discrimination training.

**5.2 Control Stimulation:** Participants will undergo a single-point discrimination training at the same sites as described above. We will employ a discrimination paradigm similar to that described by Moseley et al. (2008). Probes of different sizes will be used for this portion - a small diameter probe (~1-5 mm) and a large diameter probe (~6-50mm). The probes will be gently placed in contact with the participants' skin, and the participant will be instructed to respond if they were contacted with the small or large probe. Participants will be informed immediately of correct and incorrect responses as part of the discrimination training.

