## **1 SPECIFIC AIMS**

Pain in both youth and adults is a complex, subjective and personal experience, and remains poorly understood. One particularly perplexing dimension of some forms of pain is the tendency of pain to spread outside of an affected body site to adjacent location, and then to unaffected body sites. Such widespread pain may reflect an altered spatial tuning of somatosensory processing, such that lateral inhibition is diminished, thereby allowing pain to spread. To date, no therapies exist which are designed specifically to diminish or even reverse the spatial spread of pain. However, training in two-point discrimination holds the potential to retune spatial aspects of somatosensory processing and may represent a novel therapy for widespread pain. Thus, the present investigation will test the following aims:

**Aim 1. Do youth with chronic pain have disrupted spatial tuning of somatosensory processing?** Deficits in two point tactile discrimination have long been noted in adults with chronic pain, but such deficits remain poorly documented in pediatric chronic pain patients. In order to determine if such deficits exist, youth with both chronic pain and healthy youth will undergo assessment of two point discrimination thresholds.

**Aim 2. Does two-point discrimination training result in diminished pain and disability in youth with somatic pain?** After initial characterization of tactile discrimination thresholds, youth with chronic pain will participate in multiple sessions of either two-point discrimination training or a single-point spatially-directed attentional control condition. Training will involve up to 9 additional sessions. Efficacy of training will be assessed by 1) reductions in the spatial extent of pain, 2) reductions in pain intensity and unpleasantness, and 3) reductions in pain-related disability.

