**Aim 2:**

To maximize the utility of data collected, a mixed model analysis of variance will be utilized to determine differences between groups (between factor), differences over time (within factor), and time X group interactions.

Outcome variables of interest include 1) reductions in area of pain, 2) reductions in pain intensity and unpleasantness, 3) reductions in pain-related disability

Control variables include: 1) Improvements in tactile discrimination thresholds, 2) data from psychological questionnaires. These variables may be added as covariates to the overall model, or may be used to perform a manipulation check. JMP or R software will be used to perform analyses

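### Section 5.1 scores the two-point threshold only from 'two' reports and gives the interleaved one-point trials no role, so the Aim 1 outcome mixes acuity with willingness to say 'two'

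*Protocol*

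**What the plan says.** Section 5.1 of the protocol describes the two-point threshold as a test that "relies heavily on lateral inhibition". After series of increasing and decreasing prong distances, "the TPD will be deemed as the distance at which participants consistently report two points instead of one". The word 'consistently' has no numeric value. The section adds: "One-point stimuli will be interleaved to serve as a control condition". It states no false-report limit, correction or exclusion based on those touches, and no other section does.

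The rule stands under the training heading, but it is the only two-point scoring rule in the protocol. It is therefore the only one available for the discrimination assessments listed at Visit 1 (section 7.1) and Visit 10 (section 7.3).

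The threshold has two uses:

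- **Aim 1.** Section 1 says that "youth with both chronic pain and healthy youth will undergo assessment of two point discrimination thresholds". Section 9.1 compares the groups by mixed model analysis of variance, with body site as the within-subject factor.
- **Aim 2.** Section 9.1 says: "Control variables include: 1) Improvements in tactile discrimination thresholds, 2) data from psychological questionnaires". It allows these to serve as covariates or as a manipulation check, without requiring either.

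On feedback, section 5.1 says: "Participants will be informed immediately of correct and incorrect responses as part of the discrimination training". In the two-point arm this concerns one versus two points. In the control arm (section 5.2) the task is probe size: "the participant will be instructed to respond if they were contacted with the small or large probe".

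**The concern.** The protocol defines the threshold as an ability but scores it from a report. In a one-or-two judgement, the report depends on how well the person can tell the stimuli apart and on how much evidence the person wants before saying 'two'. One-point touches are what separate these two parts, because a 'two' on a single touch cannot reflect acuity. A rule that reads only the distance at which 'two' is reported reliably cannot distinguish a change in one part from a change in the other.

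The exposure is greatest in Aim 1, where the threshold is the outcome and a group difference would be read as disrupted spatial tuning. If patients were more cautious than healthy youth, they would show a higher threshold with no loss of acuity. If they were less cautious, a real deficit could be masked.

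In Aim 2 the exposure is smaller. Only the two-point arm practises the one-versus-two judgement with feedback, so the response criterion could move differently in the two arms. That would affect threshold change if it is used as a covariate or manipulation check.

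**Working it through.** The protocol gives no false-report rate, threshold value or numeric meaning for 'consistently', so there is no figure of its own to reproduce. The calculation below shows how the stated rule behaves when acuity is held fixed. Every input is an assumption.

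**Model (assumed).** Equal-variance signal detection with sensitivity proportional to prong distance x: d'(x) = s·x. FA is the proportion of one-point touches called 'two', and q is the proportion of 'two' reports taken as 'consistently'. z(·) is the standard normal quantile.

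**Stated rule.** The criterion is c = z(1 − FA). The chance of reporting 'two' at distance x is Φ(s·x − c). Setting this equal to q gives

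scored threshold = [z(1 − FA) + z(q)] / s.

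Acuity s cancels from any percentage change, so only FA and q matter.

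**Numerators at q = 0.75, where z(q) = 0.674:**

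| FA | z(1 − FA) | Sum |
|---|---|---|
| 5% | 1.645 | 2.319 |
| 10% | 1.282 | 1.956 |
| 20% | 0.842 | 1.516 |

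**Change in score with acuity unchanged:**

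- FA 10% to 20%: 1.516/1.956 − 1 = −22%
- FA 20% to 10%: 1.956/1.516 − 1 = +29%
- FA 20% to 5%: 2.319/1.516 − 1 = +53%

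**Sensitivity to the meaning of 'consistently' (FA 10% to 20%):**

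- q = 0.50: 0.842/1.282 − 1 = −34%
- q = 0.90, z(q) = 1.282: 2.123/2.563 − 1 = −17%

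In millimetres, with s = 0.05 per mm and q = 0.75, the 10% to 20% shift moves the score from 39.1 to 30.3 mm.

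**A score that uses the one-point trials.** In the same model, z(proportion 'two' at x) − z(FA) = (s·x − c) + c = s·x. The distance at which this equals 1 is 1/s, whatever the FA: 20 mm at s = 0.05. The correction removes the shift completely here because the model is assumed to hold. With real data it would do so only approximately.

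**Precision of the correction.** The number of one-point trials is not stated. With a true FA of 10%, 10 one-point trials yield no false report with probability 0.9^10 = 35%, and 20 yield none with probability 0.9^20 = 12%. An uncorrected d' is then undefined, so a correction for zero counts or a pooled model is needed.

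**The case against.** The strongest reply is that the protocol lacks detail here but is not wrong. Calling the one-point touches a control implies that someone will look at false 'two' reports. Section 3 also plans to optimise threshold testing in up to ten pilot participants, and the rule cites earlier studies that may handle the matter. Part of this stands: a reader might infer that one-point responses are discarded, and the protocol does not say so. But it does fix a scoring rule, that rule gives these trials no part, and neither the word 'control' nor a plan to pilot changes it. How the cited studies scored their trials cannot be judged from the protocol.

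The reply also says the mechanism is conjecture. This stands as to size and direction. No false-report data are given, nothing shows that patients hold a different criterion, and a single-point reading of the psychometric curve simplifies the increasing and decreasing series. A reader might infer that training will make participants say 'two' more freely and so create a false improvement. The text does not support that: feedback also corrects false 'two' reports and may restrain them.

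A reader might also infer that the Aim 2 treatment comparison is biased. It is not affected by this route. Its outcomes in section 9.1 are pain area, pain intensity and unpleasantness, and disability, none of which is computed from the threshold.

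Finally, a reader might suspect that feedback is given during the assessments themselves. Section 5.1 ties feedback to training, and sections 7.1 and 7.3 list assessment separately from intervention, so no change is needed there.

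**Conclusion.** The point holds in a limited form. Followed as written, section 5.1 yields a threshold that depends on response criterion as well as acuity, and Aim 1 reads it as spatial tuning. A group difference in willingness to say 'two' could produce or conceal an apparent deficit. In Aim 2 only an optional covariate or manipulation check is exposed.

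The 22% figure, with its range of 17% to 34% across readings of 'consistently', shows that a modest criterion shift could matter. It does not estimate the bias in this trial. It rests on assumed false-report rates, equal variance and sensitivity proportional to distance. This is an inexpensive improvement to the Aim 1 measure; it does not challenge the trial's efficacy analysis.

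**What to change.** In section 5.1, state that every 'two' response on a one-point trial is recorded. In section 9.1, state that the false 'two' rate is reported by group and visit.

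Also in section 9.1, analyse Aim 1, and any threshold change used in Aim 2, with a threshold corrected for that rate beside the threshold as now defined. Either of two routes would do: a d'-based threshold with a standard correction for zero false reports, or a model that pools trials across participants. Add that a threshold difference will be attributed to spatial tuning only if it holds after the correction.

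The one-point trials are already part of the procedure, so the cost is wording, recording and some analysis work. The downside is precision: corrected values are noisier if one-point trials are few. For that reason the corrected threshold should accompany the stated one and not replace it.

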## 6 STUDY PROCEDURES AND MEASURES

### 6.1 Study Recruitment/Enrollment Procedures

The primary methodology for identifying and recruiting chronic pain patients for this study will be through identification of potential participants from the inpatient and outpatient chronic pain clinics at Cincinnati Children's Hospital Medical Center, as well as community advertisements. Over the course of this project, we will enroll up to 50 patients.

Healthy control participants will be identified via word-of-mouth recruitment as well as advertisements throughout the community. We will enroll up to 30 healthy control participants.

Methods and processes for identifying patients will be conducted in accordance with the Declaration of Helsinki and Good Clinical Practice Guidelines.

To support our recruitment and retention, progress will be evaluated weekly and existing challenges and potential solutions will be discussed with the study team to ensure we meet our projected timeline.

### 6.2 Consent/Accent Procedure

Participants and parents/guardians will be given ample time to read the consent document. To ensure comprehension, the experimenter will ask a brief series of questions to ensure that both participants and/or parents/guardians understand key aspects of the study. Once comprehension has been demonstrated the participant and parents/guardian will sign the consent form. The experimenter will then sign the consent form. A copy of the signed consent form will be provided to participants' folder. This procedure will be documented on a form which will be placed in the participants' folder.

### **6.3 Participant Characterization**

Medical History: A medical history will be completed to capture pain diagnosis, medication usage, and concurrent conditions. This will be augmented and crossreferenced with information from the participant's medical record.

Body Morphometry: Height, weight, and hip and waist circumference will be obtained.

Menstrual Cycle: Position in the menstrual cycle will be noted by onset of last menstrual period in women who are not on oral contraceptives. For women on oral contraceptives, the phase of the cycle will be determined by the contraceptive pill packet.

### **6.4 Pain Assessment**

Psychophysical Assessment of Pain Magnitude: Pain intensity and pain unpleasantness will be assessed by mechanical and computerized visual analogue scales (VAS) (Price et al., 1994). These scales have been repeatedly demonstrated to 1) provide reliably separate assessment of intensity and unpleasantness, 2) to be internally consistent, and 3) to approximate ratio scale measurement accuracy (Price, 1999). Participants will be instructed in their use via a radio analogy (Price et al., 1989). These scales have been used extensively by the PI in ongoing studies in youth. We may also provide auditory stimuli via calibrated headphones (up to 95 dB for 10s) to provide a cross-modality training procedure to reinforce the concepts of intensity and unpleasantness.

Pain and Symptom Assessment Questionnaire: This questionnaire documents pain location and additional pain related symptoms.

Assessment of Pain Location: Pain location will be characterized by having the participant draw regions of pain on a paper or electronic body map or photo of themselves.

### **6.5 Psychological Assessment/Questionnaires**

Variation in psychological states can contribute substantially to the construction of the experience of pain, and may importantly influence attentional processes related to pain. Thus, participants will undergo extensive psychological characterization with a particular focus on variables known to influence pain. Many scales will be useful for enabling comparisons of these patients with chronic pain patients in other studies, and are part of our standard testing battery.

Anxiety: The PROMIS Anxiety pediatric scales will be used to assess anxiety. The SCARED anxiety scale will be used to further characterize anxiety.

Mood and Affect: The PROMIS Depression pediatric scales will be used to assess depression. The Positive and Negative Affect Schedule - Expanded will be used to characterize mood and affect.

Mindfulness: The Freiburg Mindfulness Inventory will be used to assess mindfulness.

Impulsivity: The Barratt Impulsiveness Scale will be used to assess impulsivity.

Handedness: The Edinburgh Handedness Inventory will be used to assess the degree of handedness and will be critical in the interpretation of differences in the lateralization of nociceptive processing.

Sleep: Sleep deprivation may substantially alter pain sensitivity. The Epworth Sleepiness Scale will be used to quantify the level of daytime sleepiness, while the Pittsburgh Sleep Quality Index will be used to assess sleep quality.

Pain Interference, Disability, and Catastrophizing: The PROMIS Pain Interference Scale (pediatric version) will be used to assess how much pain interferes with daily living. Pediatric versions of the pain catastrophizing scale will be used to assess pain-related catastrophizing, while the Functional Disability Index will be used to characterize disability.

Social Status and Discrimination: Insurance, income, education level, and experience of discrimination will be used to quantify socio-economic variables.

## 7 Study Visits

The duration of two-point discrimination needed to improve pain remains completely unknown. To optimize retention, we may truncate the number of visits, depending on subject availability, with procedures in Visit 10 being performed at the final visit. Healthy control participants will only participate in the baseline visit.

### 7.1 Baseline + Intervention - Visit 1 (up to 3 hours)

- Completion of informed consent/assent prior to initiation of study procedures
- Obtain information for payment, provide ClinCard
- Randomize to intervention
- Review medical history
- Document all concomitant medications including prescribed, over the counter, and nutraceutical supplements
- Administer questionnaires
- Assess pain intensity, unpleasantness, qualitative aspects of pain
- Assess spatial extent of pain (body map or patient's own photo)
- Demonstration of two-point/single-point discrimination procedure
- Assess two-point/single-point discrimination
- Initiate intervention (TPD training or Control)
- Assess pain intensity, unpleasantness
- Assess spatial extent of pain

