## **3 STUDY DESIGN**

Prior to commencing this investigation we will optimize the tactile discrimination threshold testing (i.e. as per baseline visit, below), and the training conditions, in up to ten participants (patients and/or healthy controls). This will serve as a pilot to refine operational aspects of study procedures before we commence the main investigation proposed herein. Following this, youth with either chronic pain (ages 10-17, n=40) or healthy youth (ages 10-17, n=20) will undergo assessments of two-point and single-point discrimination thresholds in an initial session (Aim 1). After this initial session, youth with chronic pain will participate in up to 9 additional sessions of attentional training (Aim 2). These chronic pain patients will be randomized to either two-point discrimination training (n=20) or a single-point spatially-directed attentional control condition (n=20). Participants will not be informed of which intervention they will receive (single-blind study). Psychological questionnaires will be completed in the first and last sessions in order to determine how these variables relate to tactile discrimination and response to training.

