**7.3. Intervention+Completion - Visit 10 (up to 3 hours)**

Assess pain intensity, unpleasantness, qualitative aspects of pain  
Assess spatial extent of pain  
Final intervention (TPD training or Control)  
Assess two-point/single-point discrimination  
Assess pain intensity, unpleasantness, qualitative aspects of pain  
Assess spatial extent of pain  
Administer psychological questionnaires

Note that some of the procedures above may be omitted for the purpose of streamlining the study visits, or if procedures are deemed to be incongruent with the participants' ongoing clinical treatments. Omitting these procedures would reduce participant burden and would have no impact on safety.

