**9. STATISTICS**

**9.1 Statistical Analysis Plan**

**Aim 1:**

A mixed model analysis of variance will be utilized to determine differences between groups (chronic pain patients vs. healthy controls - between factor) and body site (within factor), and group X body site interactions.

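### Section 7.1 places randomisation ahead of every baseline assessment in a trial that blinds participants only; drawing the arm just before training would keep the baseline and the Aim 1 comparison free of arm knowledge at negligible cost (minor)

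*Protocol*

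**What the plan says.** Protocol section 7.1 lists the Visit 1 steps. After consent and payment set-up comes "Randomize to intervention". Medical history, medications, questionnaires, pain ratings, body map, the demonstration of the discrimination procedure and the discrimination assessment all follow it. Only then comes "Initiate intervention (TPD training or Control)", and pain and body map are taken once more.

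On blinding, section 3 says: "Participants will not be informed of which intervention they will receive (single-blind study)". The protocol does not say whether the examiner knows the arm, or when.

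Section 3 makes the initial threshold the Aim 1 measure: patients and healthy youth "will undergo assessments of two-point and single-point discrimination thresholds in an initial session (Aim 1)". Section 9.1 analyses Aim 1 as "differences between groups (chronic pain patients vs. healthy controls - between factor)". For Aim 2, section 9.1 names improvement in tactile threshold as a control variable, for possible use as a covariate or manipulation check. The outcomes there are pain area, pain intensity and unpleasantness, and disability.

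Section 5.1 describes the threshold procedure: caliper distance is moved down and up repeatedly, and "the TPD will be deemed as the distance at which participants consistently report two points instead of one". Section 7.3 repeats the measurement at the last visit: "Assess two-point/single-point discrimination". Section 7 notes that "Healthy control participants will only participate in the baseline visit".

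**The concern.** Followed in the order given, the list lets the examiner know a patient's arm while demonstrating the task and taking the baseline threshold. Placing the calipers, stepping the distance and judging what counts as consistent reporting are in the examiner's hands. Knowledge of the arm could affect any of them, without intent.

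Three things are at stake. First, a shift d in one arm's baseline threshold enters that arm's change in full if the final value is not shifted too, so the manipulation check or covariate could show a difference in tactile improvement that training did not cause. Second, the same shift moves the mean of all patients by d/2 in the Aim 1 comparison with healthy controls, who have no arm. Third, a patient who leaves between randomisation and baseline is a randomised patient with no baseline, which matters with 20 per arm. None of this exposure is needed, because the arm is not used until training starts.

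**Working it through.** **Is the list a time sequence?** It is not labelled as one, but it reads as one. Consent precedes study procedures, the demonstration precedes the assessment, and pain and body map appear before training and again after it. Section 1 (Aim 2) and section 3 place training after the initial threshold assessment, but neither says when the arm is drawn. Section 7.1 is therefore the only text that places randomisation, and it places it early.

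**Does anything offset the order?** Section 3 withholds the arm from participants. No section withholds it from the examiner, or holds the next allocation back until baseline is complete.

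**How large could the effect be?** The protocol gives no shift, SD or correlation, so what follows is a sensitivity illustration.

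Inputs from the protocol: 20 patients per arm and 20 healthy controls (section 3); significance at 0.05 (section 9.3), taken as two-sided. Assumed: no true effect; a shift d of 0.1, 0.2 or 0.3 SD in one arm's baseline only; a correlation ρ of 0.5 or 0.7 between baseline and final threshold; one body site.

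*Aim 2 threshold change.* With two occasions, the group-by-time test is a two-sample t-test on the change, with 38 degrees of freedom. In SD units of a single measurement:

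- SD of the change = √(2(1 − ρ)), which is 1.000 at ρ = 0.5 and 0.775 at ρ = 0.7.
- Noncentrality = d / (SD of change × √(2/20)). At d = 0.3 this is 0.3 / (1.000 × 0.316) = 0.949 for ρ = 0.5, and 0.3 / (0.775 × 0.316) = 1.225 for ρ = 0.7.

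| d (SD) | False positives, ρ = 0.5 | False positives, ρ = 0.7 |
|---|---|---|
| 0 | 5% | 5% |
| 0.1 | 6.1% | 6.8% |
| 0.2 | 9.5% | 12.5% |
| 0.3 | 15.2% | 22.3% |

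Simulation with 40,000 runs gave 6.1, 9.4 and 15.1% at ρ = 0.5, and 6.7, 12.3 and 22.5% at ρ = 0.7.

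*Aim 1.* Of the 40 patients, 20 are shifted by d, so the patient mean moves by d × 20/40 = d/2. Noncentrality = (d/2) / √(1/40 + 1/20) with 58 degrees of freedom. At d = 0.3 this is 0.15 / 0.274 = 0.548.

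| d (SD) | Shift in patient mean (SD) | False positives |
|---|---|---|
| 0.1 | 0.05 | 5.4% |
| 0.2 | 0.10 | 6.5% |
| 0.3 | 0.15 | 8.4% |

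Averaging over two or three body sites, with an assumed between-site correlation of 0.5 to 0.7, gives 9.0 to 10.1% at d = 0.3.

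*Two boundary cases for the Aim 2 change.* If only the final value is shifted by d, the noncentrality and the rates are the same as in the first table. If baseline and final values in one arm are both shifted by d, the change moves by d − d = 0 and the rate is 5%.

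**The case against.** The strongest reply is that the defect is mostly silence. The protocol never says that the examiner is told the arm at the third step, and the order of a checklist causes no bias by itself. The list also serves healthy controls, who are never randomised, so it is not a literal sequence for everyone. This stands as a limit: the finding is that nothing prevents the exposure, not that it occurs. It does not remove the point, because the order written down is worse than one available within the same visit.

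The second reply is that the threshold is not an efficacy outcome. This also stands. A reader might infer that the efficacy comparison carries a 6 to 22% false-positive rate. The protocol does not support that: the outcomes in section 9.1 are largely reported by participants who are not told their arm, and the threshold enters Aim 2 only as an optional covariate or manipulation check.

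The third reply is that protecting baseline alone need not improve the Aim 2 threshold change. If an examiner who knows the arm shifts both visits equally, the shift cancels; with only baseline protected, the final shift no longer cancels. This is correct, and opposite shifts would favour the change. The protocol cannot say which applies.

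Finally, section 5.1 interleaves one-point stimuli and repeats the stepping in both directions, and section 3 foresees a pilot to optimise threshold testing. These features limit the examiner's influence but do not exclude it, and section 5.1 describes training, not the baseline test as such.

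**Conclusion.** The point holds as a minor design weakness. Section 7.1 draws the arm before any baseline measurement, section 3 blinds participants only, and nothing keeps the arm from the examiner until training begins. The sure gain from changing the order is a baseline, and an Aim 1 comparison, that knowledge of the arm cannot influence, with no patient lost between randomisation and baseline.

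The size of any bias is unknown. The ranges of 6 to 22% for the threshold change and 5.4 to 8.4% for Aim 1 rest on assumed shifts of 0.1 to 0.3 SD in one arm's baseline only, assumed correlations of 0.5 to 0.7 for the change, and one body site. A reader might infer that the new order secures an unbiased Aim 2 threshold change. It does not, because thresholds at the final visit stay exposed and a shift common to both visits would have cancelled. A reader might also infer that the reordering is worthless without a concealment statement. That goes too far: an arm not yet drawn cannot be known unless the next allocation is predictable or visible. The statement closes that remaining gap.

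**What to change.** In section 7.1, for chronic pain patients only, move the randomisation step to directly before the start of the intervention, after all pre-training assessments including two-point/single-point discrimination. Add one sentence saying that the next allocation is not visible to the examiner until that step. Add a second saying that assessments made after training starts, including the final-visit threshold in section 7.3, are not protected by this and may be taken by staff who know the arm.

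The cost is negligible. Visits, procedures, sample size and power are unchanged. The only new demand is that someone or something holds the allocation until mid-visit; the protocol does not describe how allocations are issued, so that small burden cannot be put at exactly zero. If staff already randomise late, the edit makes the document match practice.
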